Newborns, particularly those requiring hospitalization due to preterm birth, low birth weight, or severe intestinal dysfunction, are exposed to scenarios markedly different from the general population. In neonatal intensive care units (NICUs), life support and nutritional supply are highly dependent on plastic medical devices such as intravenous infusion bags, tubing, infusion pumps, and ventilator circuits. These devices may contain intentionally added microplastics during production or release secondary microplastics through physical friction or chemical degradation during use. Of particular significance is that for critically ill neonates who cannot be fed orally, parenteral nutrition (PN) serves as their sole source of survival. However, the entire "plastic tubing" system constituting the parenteral nutrition delivery pathway represents a potential, persistent source of microplastic exposure. Studies have demonstrated that microplastic particles can be detected in infusion solutions after passing through plastic equipment^[1]. This implies that neonates receiving intravenous nutrition may be subjected to a unique exposure pattern of "iatrogenic, persistent microplastic infusion."

However, clinical studies on neonatal exposure to AP remain limited. Moreover, most neonatal biomonitoring studies are based on in vitro experiments and random urine samples collected at hospital admission or discharge, without considering the time-dependent nature of exposure. Additionally, there is a lack of research on neonatal microplastic load, particularly quantitative data in blood. Therefore, this study aims to assess the current status of neonatal microplastic exposure during NICU hospitalization. Through a meticulously designed gradient exposure cohort, this study seeks to systematically evaluate and compare the microplastic load in the blood of neonates receiving long-term parenteral nutrition for the first time.

2. Materials and Methods

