2.1. Study Population and Stratification

This study was a prospective observational study. In 2025, 12 neonates were enrolled in the NICU of the Second Affiliated Hospital of Guangdong Province, Jinan University. All

subjects mothers had no underlying conditions such as heart disease, chronic kidney disease, mental illness, hypertension, diabetes, gestational hypertension, or gestational diabetes. Researchers conducted face-to-face interviews to record demographic information. All participants signed informed consent forms and completed questionnaires. A total of 12 neonatal blood samples, 12 breast milk samples, and 12 bottle milk samples were collected. To accurately assess the dose-response relationship between the duration of parenteral nutrition and microplastic load, neonatal blood samples were divided into the following three groups: (1) Long-term exposure group (n=4): Preterm infants requiring total parenteral nutrition support for >14 days due to severe feeding difficulties, necrotizing enterocolitis (NEC), short bowel syndrome, or other serious intestinal diseases. (2) Short-term exposure group (n=4): Preterm infants receiving total parenteral nutrition support for 3 to 7 days due to early adaptation issues (e.g., respiratory distress, transient feeding intolerance) and having successfully transitioned to total enteral nutrition for at least 48 hours prior to blood sample collection. This group represented common, transient, routine iatrogenic exposure in NICUs. Control group (n=4): The cohort consisted of healthy full-term neonates with gestational age \geq 37 weeks. These infants received no intravenous nutritional support or planned fluid therapy, serving as baseline microplastic levels in the absence of relevant iatrogenic exposure. The study strictly adhered to the ethical guidelines of the Declaration of Helsinki, and the protocol was approved by the Medical Ethics Committee of the Second Affiliated Hospital of Guangdong Province, Jinan University.

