2.2 Interview Content

At enrollment, investigators conducted interviews to collect demographic information from newborns and pregnant women, including education level (high school or below, bachelors degree, masters degree or above), per capita annual income (<100,000 yuan, 100,000-200,000 yuan, >200,000 yuan), occupation (government official, professional technician, general clerk, commercial service, other), number of pregnancies (primipara, multipara), mode of pregnancy (natural delivery, assisted delivery), delivery outcome (preterm, full-term), delivery method (vaginal delivery, cesarean section), newborn gender (male, female), and neonatal weight. Details are provided in Table S1.

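### The long-term and short-term PN groups differ in indication and in time since last PN as well as in duration, and no reporting of other device exposure is planned, so their contrast cannot be attributed to PN duration alone

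*Combined protocol and SAP*

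**What the plan says.** Section 2.1 gives the purpose of the grouping: "To accurately assess the dose-response relationship between the duration of parenteral nutrition and microplastic load". It then defines two preterm groups.

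- "Long-term exposure group (n=4"): more than 14 days of total PN, "due to severe feeding difficulties, necrotizing enterocolitis (NEC), short bowel syndrome, or other serious intestinal diseases".
- "Short-term exposure group (n=4"): 3 to 7 days of total PN, "due to early adaptation issues (e.g., respiratory distress, transient feeding intolerance"), with full enteral feeding for at least 48 hours before the blood sample. No such condition is set for the long-term group.

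Section 1 (Background) says that NICU life support and nutrition rely on "plastic medical devices such as intravenous infusion bags, tubing, infusion pumps, and ventilator circuits", and that such devices may contain or shed microplastics.

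For the infant and the delivery, section 2.2 lists "delivery outcome (preterm, full-term), delivery method (vaginal delivery, cesarean section), newborn gender (male, female), and neonatal weight". The Survey Form carries the same items. Section 2.4 plans baseline comparisons across the three groups, and then correlation (cor.test) and Wilcoxon tests (wilcox.test). It mentions no adjustment, matching or stratification.

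**The concern.** A dose-response reading of long versus short needs the two groups to be comparable in everything else that could put microplastics into the blood. Here the reason for PN is part of each group's definition, and the reasons point to different care. Serious intestinal disease suggests more non-PN infusions; respiratory distress suggests more time on a ventilator circuit. The protocol itself counts both kinds of equipment as sources.

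Time since last PN is also tied to group, because a PN-free interval before sampling is required in one group only.

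A higher load in the long-term group could reflect PN duration, other intravenous therapy, or sampling closer to the last infusion. A similar load in both groups could hide a PN effect offset by respiratory support in the short-term infants. The planned baseline table would not show which. This problem lies between the two preterm groups, so it would remain even if the comparison with full-term controls were repaired.

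**Working it through.** The documents give no sample-size, power or effect-size figure to reproduce. The main check is of the text; the arithmetic only shows what would follow under stated assumptions.

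**What separates the two PN groups (section 2.1)**

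| Feature | Long-term (n=4) | Short-term (n=4) |
|---|---|---|
| Total PN | more than 14 days | 3 to 7 days |
| Indication | serious intestinal disease or severe feeding difficulty | early adaptation problems |
| Full enteral feeding before sampling | no condition | at least 48 hours |
| Preterm | all | all |

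Three features change together and only the first is the exposure of interest. Preterm/full-term takes one value in all 4 + 4 = 8 PN infants, so it cannot describe any difference between them.

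**What the plan lists that could reveal an imbalance (section 2.2, Survey Form)**

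For these 8 infants, the items bearing on the infant's condition reduce to weight, with no time point given. Diagnosis, respiratory support, non-PN infusions, transfusion, surgery, gestational age in weeks, age at sampling and time since last PN are not listed.

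**What another device-related factor could do to the test**

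Assumptions: a two-sided exact Wilcoxon test of long versus short at 0.05, no ties, normal data with SD 1, 200,000 simulated runs per setting. There are C(8,4) = 70 equally likely rank arrangements under the null. The smallest p is 2/70 = 0.029, reached only when the groups separate completely; the next is 4/70 = 0.057. The test therefore rejects only on complete separation.

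With no PN-duration effect and an assumed shift in one group from other devices:

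| Assumed shift (SD) | 0 | 0.5 | 1 | 1.5 | 2 | 3 |
|---|---|---|---|---|---|---|
| Rejection rate | 2.9% | 5.4% | 13.9% | 29.3% | 48.9% | 83.1% |

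With an assumed true PN effect of 2 SD and a shift in the opposite direction:

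| Opposing shift (SD) | 0 | 0.5 | 1 | 1.5 | 2 |
|---|---|---|---|---|---|
| Rejection rate | 48.9% | 29.5% | 14.3% | 5.5% | 2.8% |

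**Whether adjustment could repair it**

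Take one yes/no factor, such as ventilated or not, and stratify the exact test on it.

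- Each group splits 2 + 2: C(4,2) × C(4,2) = 36 arrangements, smallest p = 2/36 = 0.056.
- One group splits 3 + 1 and the other 1 + 3: C(4,3) × C(4,1) = 16 arrangements, smallest p = 2/16 = 0.125.

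Neither can reach 0.05. Recording these factors supports description, not adjusted inference.

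**The case against.** The strongest reply is that nothing in the text shows that device exposure differs. Section 2.1 sets groups by PN duration and indication, not by ventilation or other infusions. Respiratory distress is only an example, so a short-term infant may qualify on feeding intolerance alone. Nothing rules out ventilation in the long-term infants, and the two feeding indications lie close together. This stands. A reader might infer that other device exposure differs by definition, or that the results of all 8 PN infants are biased; the documents support neither. Indication differs by definition, while different device exposure is a plausible inference.

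A reader might also infer that none of this information will exist. That goes too far. Section 2.2 covers an interview, and the listed items omit PN duration and indication, which must be known to assign groups. Gestational age must likewise be known to apply the 37-week rule for controls. Other records are evidently in use. What can be said is that the plan does not state that device exposure will be abstracted or reported.

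Nor does the protocol say that the two groups should differ only in PN duration. The Background also frames the aim as describing exposure during the NICU stay. But the dose-response purpose is stated outright in section 2.1, and it is that purpose which the contrast cannot serve.

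Finally, a null result needs no confounding to explain it: under the assumptions above, even a 2 SD effect is detected only about 49% of the time. This weakens any claim that ventilator exposure would be the cause of a null, but it gives no help in attributing a result to PN duration.

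**Conclusion.** The point holds as a limit on attribution. Indication and the pre-sampling interval are tied to group by the text itself. Differing exposure to other devices is inferred from the indications together with the protocol's own list of sources. The plan neither reports nor allows for any of these, so a long-versus-short result, positive or null, cannot be assigned to PN duration alone.

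The size of any bias cannot be computed and its sign could go either way. The rejection rates of 3% to 83% rest on assumed shifts of 0 to 3 SD; they show what a bias of that size would do and are not evidence that one is present. More infants recruited under the same definitions would not remove the problem, because the indication is built into the groups.

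**What to change.** From the existing charts, up to the blood draw, abstract for each infant where applicable: PN indication; days of invasive respiratory support; days of non-invasive respiratory support; days of non-PN intravenous therapy (volume too if readily available); transfusions; surgery; gestational age in weeks; age at sampling; and time since last PN. Show these per infant beside the microplastic load, and use gestational age in weeks in place of preterm/full-term when describing the two PN groups. Do not fit an adjusted model.

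State the long-versus-short result as a descriptive difference in NICU device exposure between infants needing long and short PN. Reserve wording about an effect of PN duration for the case where the groups are shown to overlap on these factors.

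The cost is nine fields for 12 infants, at most 9 × 12 = 108 entries, and a claim less specific to PN. Section 2.3 (Sample Collection) says the samples are anonymized, so the chart link has to be made while it still exists. Choosing more comparable short-term infants is not offered as a remedy, because section 2.1 describes the 12 as already enrolled.

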2.3 Sample Collection

Samples were collected by trained pediatricians and pediatric nurses. After delivery, the newborns blood was drawn using a non-plastic blood collector and then injected into a glass anticoagulation tube (KERONG, 3mL, China Chengdu). Breast milk and milk from bottles were collected by trained nurses or family members and quickly placed into sample boxes. To avoid contamination, all consumables that came into contact with the samples during the sampling process were non-plastic products. All samples were stored in a -80°C environment and strictly anonymized.

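### Term controls without PN cannot be the zero-dose baseline for a PN-duration dose-response, because every PN infant is preterm and every control is term

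*Combined protocol and SAP*

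**What the plan says.** Section 2.1 gives the purpose of the grouping: "To accurately assess the dose-response relationship between the duration of parenteral nutrition and microplastic load". The Background describes the design in the same spirit: "Through a meticulously designed gradient exposure cohort". The three groups, four infants each, are:

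- **Long-term:** preterm, total PN for more than 14 days, because of severe feeding difficulties, NEC, short bowel syndrome or other serious intestinal disease.
- **Short-term:** "Preterm infants receiving total parenteral nutrition support for 3 to 7 days due to early adaptation issues", and "having successfully transitioned to total enteral nutrition for at least 48 hours prior to blood sample collection". No matching PN-free interval is set for the long-term group.
- **Control:** "The cohort consisted of healthy full-term neonates with gestational age" of at least 37 weeks. Their role is stated as: "These infants received no intravenous nutritional support or planned fluid therapy, serving as baseline microplastic levels in the absence of relevant iatrogenic exposure".

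Section 2.2 (Interview Content) and the survey form record maturity only as a two-level item, "delivery outcome (preterm, full-term"). Section 2.4 (Statistical Analysis) assigns ANOVA, Kruskal-Wallis and Fisher tests to baseline comparisons. It then names cor.test and wilcox.test without saying which variables enter them. It mentions no adjustment, matching or restriction to preterm infants.

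**The concern.** A dose-response needs infants who differ in PN exposure but are otherwise comparable. Here no preterm infant is without PN and no term infant has it. The controls also differ from the PN groups in illness and, to an undocumented degree, in other NICU plastic exposure. The Background itself names ventilator circuits and infusion pumps as sources, whereas the control definition rules out only intravenous nutrition and planned fluids.

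If preterm or sick infants carry a different load for reasons unrelated to PN, the controls will sit apart from both PN groups. Under the stated aim that would be read as a PN gradient. The study would also appear to have 12 infants' worth of evidence on duration when it has 8.

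**Working it through.** **Inputs from Section 2.1.** Groups of 4 + 4 + 4 = 12; preterm infants 4 + 4 = 8; PN days 0 (control), 3 to 7 (short), more than 14 (long). The documents give no effect size, SD, power or longest PN duration, so there is no planned figure to reproduce.

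**Step 1: what can be estimated.** Let π be the preterm-versus-term difference, and τS and τL the effects of short and long PN. The expected group means are:

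- control: μ
- short: μ + π + τS
- long: μ + π + τL

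Hence short − control = π + τS, long − control = π + τL, and long − short = τL − τS. In matrix terms the preterm column equals short + long, so [intercept, short, long, preterm] has rank 3 of 4. Appending the long-minus-short contrast leaves the rank at 3 (estimable). Appending the short, long or preterm coefficient alone raises it to 4 (not estimable). The recorded maturity item is the aliased variable itself, so adjusting for it cannot separate π from τ.

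**Step 2: what the controls contribute to a slope.** In the model [intercept, PN days, preterm], rank 3 of 3, the controls all have PN days = 0 and preterm = 0. The intercept therefore fits their mean, and the 8 preterm infants have their own free intercept. The PN-days slope equals the slope in the 8 alone (checked on one data set: −0.0090878 both ways). Residual degrees of freedom are 12 − 3 = 9 instead of 8 − 2 = 6. The controls can thus inform the standard error, if variances are equal, but not the slope.

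With group scores 0, 1, 2, the total sum of squares of the score is 4 × (1 + 0 + 1) = 8. Within the preterm infants it is 8 × 0.5² = 2. So 75% of the leverage in an unadjusted trend depends on the term controls. Group means of 0, d, d, which are a pure preterm step, give a fitted slope of d/2 per group.

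**Step 3: illustration of size.** Assumptions: no PN effect; normal errors on the log scale, SD 1; the same shift added to both PN groups; short PN 3 to 7 days; long PN from 15 days to an upper limit of 20, 30, 40 or 60. Percent significant at two-sided 0.05:

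| Preterm shift (SD) | 0 | 0.5 | 1 | 2 | 3 |
|---|---|---|---|---|---|
| Spearman, 12 infants, PN days | 5 | 9 | 21 | 55 | 76 |
| Exact Wilcoxon, long v control | 3 | 5 | 14 | 49 | 83 |
| PN-days slope with preterm term | 5 | 5 | 5 | 5 | 5 |
| Exact Wilcoxon, long v short | 2.9 | 2.9 | 2.9 | 2.9 | 2.9 |

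The Spearman row hardly changes with the upper limit on PN days. Pearson does depend on it: 16% down to 10% at 1 SD and 59% down to 25% at 3 SD as the limit rises from 20 to 60 days.

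**Step 4: what the 8 preterm infants can show.** At 4 versus 4 there are 70 rank arrangements. The smallest two-sided exact p is 2/70 = 0.029, which requires complete separation; the next is 4/70 = 0.057. A long-short difference of 1, 2 or 3 SD is detected in 14%, 49% or 83% of studies. That difference need not be PN. Indication differs by definition, and the 48-hour PN-free condition applies to one group only. Age at sampling is also likely to differ: at least 3 + 2 = 5 days in the short-term group against more than 14 days in the long-term group, if infants are sampled after qualifying.

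**The case against.** The plan never says that a 12-infant correlation with controls at zero days will be run, because Section 2.4 names functions and not variables. The shifts, the log-normal errors and the long-group PN days are all assumed. Spearman is the less favourable choice; Pearson gives lower rates. A pure preterm effect also produces a step, not a gradient. In the simulation roughly a fifth, 30% and 37% of significant positive Spearman results at 1, 2 and 3 SD had a long-group median at or below the short-group median, so plain group summaries would expose part of the error. Finally, the Background also frames the aim as assessing current exposure and comparing loads, and term controls serve that purpose.

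Much of this stands as a limit on the percentages, which should be read as illustration only. It does not touch Step 1, which needs no assumed shift and applies to any control contrast under any test. The descriptive value of the controls is accepted. What Section 2.1 claims for them goes further: an accurate dose-response with the controls as its baseline.

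**Conclusion.** The concern holds and must be fixed. From the group definitions alone, a difference between controls and either PN group cannot be attributed to PN, with or without adjustment for preterm status. An unadjusted three-group trend or 12-infant correlation inherits the same fault. A model of PN days plus preterm status is protected against a preterm shift, but its slope comes entirely from the 8 preterm infants.

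The size of the resulting error cannot be derived from the documents. Under the stated assumptions a preterm shift of 1 to 3 SD turns a nominal 5% into about 21% to 76% (Spearman) or 10% to 59% (Pearson, depending on shift and PN range). The usable duration evidence is 4 versus 4, confounded by indication, age and time since last PN. The controls remain a reasonable descriptive reference.

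**What to change.** 1. Base any statement about PN duration on the 8 preterm infants (long versus short, or PN days within them). Report it as an exploratory association that also carries indication, age at sampling and time since last PN.
2. Do not run an unadjusted correlation or trend with controls entered as zero PN days. If all 12 are modelled, include a preterm term and state that the slope comes from the 8.
3. Label control contrasts as a descriptive comparison of preterm infants receiving PN with healthy term infants. Limit the claim of no relevant iatrogenic exposure to intravenous nutrition and planned fluids.
4. List for each infant, beside the blood load: gestational weeks, age at sampling, PN days, time since last PN and other device exposure. Section 2.3 (Sample Collection) says samples are strictly anonymized, so this depends on coded linkage that the plan should confirm. Without it, give group ranges.
5. State as a limitation that the study has no preterm infants without PN.

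The cost is wording in Sections 2.1 and 2.4 and five chart fields for 12 infants, with no new samples. If linkage does not exist, PN days within the 8 cannot be analysed and only long versus short remains. The price is a narrower, exploratory claim resting on 8 infants.

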2.2 Interview Content

At enrollment, investigators conducted interviews to collect demographic information from newborns and pregnant women, including education level (high school or below, bachelors degree, masters degree or above), per capita annual income (<100,000 yuan, 100,000-200,000 yuan, >200,000 yuan), occupation (government official, professional technician, general clerk, commercial service, other), number of pregnancies (primipara, multipara), mode of pregnancy (natural delivery, assisted delivery), delivery outcome (preterm, full-term), delivery method (vaginal delivery, cesarean section), newborn gender (male, female), and neonatal weight. Details are provided in Table S1.

2.3 Sample Collection

Samples were collected by trained pediatricians and pediatric nurses. After delivery, the newborns blood was drawn using a non-plastic blood collector and then injected into a glass anticoagulation tube (KERONG, 3mL, China Chengdu). Breast milk and milk from bottles were collected by trained nurses or family members and quickly placed into sample boxes. To avoid contamination, all consumables that came into contact with the samples during the sampling process were non-plastic products. All samples were stored in a -80°C environment and strictly anonymized.

